## 5 Amendments and updates

Version 2.0 (dated 18 August 2015)

- Due to more data becoming available during the protocol development, end of the study period has been extended to 31 Dec 2014 in each country. Estimated cohort sizes and power calculations have been updated accordingly.
  - Dimethyl fumarate (N07XX09) has been added to MSDMD list and removed from study limitations, as it gained market authorisation on 30 January 2014.
  - Peginterferon beta-1a (L03AB13) has been added to MSDMD list as it gained market authorisation on 18 July 2014.
- Potential confounding factors
  - Maternal age has been defined at LMP instead of previous definition at LMP / spontaneous abortion / ectopic pregnancy depending on the pregnancy outcome. Missing information with regard to maternal age at LMP has been described in Section 9.9.

- Missing data (section 9.7.7)
  - Robustness of the variable selection procedure (section 9.7.3.) to missing data will be tested as part of the sensitivity analyses.

## 6 Milestones

Milestone	Planned date*
Registration in the EU PAS register (reference date)	31 October 2015
Start of data collection (Data permit applications sent)	+ 1 month from the reference date
End of data collection (Data received)	+ 12 months from the reference date
Final report of study results	+ 24 months from the reference date

\* Dates depend on the time required to handle data permit applications and extraction of study data from the healthcare registers which are beyond the control of the investigators.

## 7 Rationale and background

MS is the most common chronic neurologic disability in young adult females of childbearing age (Baird & Dalton 2013). Women with MS are confronted with questions relating to pregnancy and pharmacological MS therapy. It is commonly understood that MS relapses are fewer during pregnancy, but also that medication taken before conception or in early pregnancy could negatively affect the outcome of the pregnancy. Experience with exposure to IFN- $\beta$  products during pregnancy has shown no clear association of adverse outcomes such as low birth weight (LBW), congenital anomaly or spontaneous abortion (Lu et al. 2012). However, it is contraindicated to initiate treatment with IFN- $\beta$  products during pregnancy. It is also recommended that if a woman becomes pregnant during treatment, she should be informed of the potential hazards and discontinuation of therapy should be considered. In patients with a high relapse rate before treatment start, the risk of a severe relapse following discontinuation of IFN- $\beta$  in the event of pregnancy should be weighed against a possible increased risk of spontaneous abortion. There are little data on newer MSDMD substances (e.g. fingolimod) (Lu et al. 2012).

This study addresses a request from the European Medicines Agency's CHMP to identify pregnancy outcomes in the MS population unexposed to IFN- $\beta$  products for comparison with the ongoing European IFN- $\beta$  Pregnancy Registry sponsored by the four European MAHs of IFN- $\beta$ s.

## 8 Research questions and objectives

This study is a population-based cohort study based on register data from three Nordic countries: FIN, SWE and NOR. The overall research questions of this study are to determine if exposure to IFN- $\beta$  before or during pregnancy has an adverse effect on pregnancy outcomes in patients with MS (ICD-10 G35) and, as requested by the CHMP, to identify the prevalence of adverse pregnancy outcomes in MS women unexposed to IFN- $\beta$  products. The cohorts from this study will provide background prevalence information and context for pregnancy outcomes in MS for the European IFN- $\beta$  Pregnancy Registry. However, the estimated prevalence from this study will not be directly compared with those from the European IFN- $\beta$  Pregnancy Registry as: First, available information on disease severity and other confounding factors differs between the health registers and the European IFN- $\beta$  Pregnancy Registry and in some cases is missing, such that the rates cannot be adjusted to be comparable. Secondly, the pregnancy cases included in the Nordic health registers are population-wide and are not based on a sample, whereas the European IFN- $\beta$  Pregnancy Registry is based on spontaneous reports.

The prevalence of the various pregnancy outcomes will be estimated in the study cohorts described below and in Table 1 (see section 9.4 for definition of exposure):

1. Women with MS exposed to IFN- $\beta$  only (i.e. these women have not been exposed to other MSDMDs) before or during pregnancy (cohort 1),
2. Women with MS exposed to IFN- $\beta$  regardless of exposure to other MSDMDs before or during pregnancy (cohort 2),
3. Women with MS unexposed to any MSDMD before or during pregnancy (cohort 3),
4. Women with MS unexposed to IFN- $\beta$  regardless of exposure to other MSDMDs before or during pregnancy (cohort 4),
5. Women exposed to MSDMDs except IFN- $\beta$  or glatiramer acetate (Copaxone®) or dimethyl fumarate (Tecfidera®) (cohort 5),
6. Women from the general population in FIN, SWE and NOR without MS diagnosis (cohort 6).

**Table 1: Definition of the study cohorts according to exposure to IFN- $\beta$  and other MSDMDs.**

Exposure status by IFN- $\beta$ and other MSDMD	Women with MS			Women without MS
	Unexposed to other MSDMD	Exposed to other MSDMD	Total	
Exposed to IFN-<math>\beta</math>	Cohort 1 Exposure to IFN- $\beta$ only	Exposed to both IFN- $\beta$ and other MSDMD (group not studied)	Cohort 2 All patients with IFN- $\beta$ exposure regardless of exposure to other MSDMDs	NA
Unexposed to IFN-<math>\beta</math>	Cohort 3 No exposure to any MSDMDs	Cohort 5 Only other MSDMD excluding IFN- $\beta$ or glatiramer acetate (Copaxone®) or dimethyl fumarate (Tecfidera®)  (for sensitivity analysis only)	Cohort 4 All patients with no IFN- $\beta$ exposure regardless of exposure to other MSDMDs	Cohort 6 Women from the general population without MS diagnosis

**The primary objectives** are:

1. To estimate the prevalence of the following pregnancy outcomes in the above four study cohorts 1 – 4:
  - Serious adverse pregnancy outcome defined as a composite endpoint including elective TOPFA, MCA or stillbirth
  - Elective TOPFA or elective termination for other reasons (assessment not possible in SWE as no register available)
  - Stillbirth
  - Live birth
  - MCA
2. To compare the prevalence of each of the outcomes in objective 1 between:
  - i) women with MS exposed to IFN- $\beta$  only (cohort 1) vs. unexposed to any MSDMDs (cohort 3) and
  - ii) women with MS exposed to IFN- $\beta$  only (cohort 1) vs. unexposed to IFN- $\beta$  regardless of exposure to other MSDMDs (cohort 4).

**The secondary objectives** are:

3. To compare the prevalence of the following pregnancy outcomes between:
  - i) women with MS exposed to IFN- $\beta$  regardless of exposure to other MSDMDs (cohort 2) vs. unexposed to any MSDMDs (cohort 3):
    - Serious adverse pregnancy outcome
    - Elective TOPFA or elective termination for other reasons (not possible in SWE)
    - Stillbirth
    - Live birth
    - MCA
4. To estimate the prevalence of a) ectopic pregnancies and b) spontaneous abortions in the study cohorts 1, 2, 3 and 4 and to compare these prevalences separately between:
  - i) women with MS exposed to IFN- $\beta$  only (cohort 1) vs. unexposed to any MSDMDs (cohort 3),
  - ii) women with MS exposed to IFN- $\beta$  only (cohort 1) vs. unexposed to IFN- $\beta$  regardless of exposure to other MSDMDs (cohort 4), and
  - iii) women with MS exposed to IFN- $\beta$  regardless of exposure to other MSDMDs (cohort 2) vs. unexposed to any MSDMDs (cohort 3).This objective is subject to available data from each country, as only information on ectopic pregnancies or spontaneous abortions requiring treatment in hospitals is available in the study.
5. To estimate the prevalence of the pregnancy outcomes (i.e. serious adverse pregnancy outcome, elective TOPFA (not possible in SWE), stillbirth, live birth and MCA) in cohorts 1 – 4 stratified by country, year of pregnancy outcome, maternal age at LMP, chronic diseases, exposure to any teratogenic medications including steroids, time since MS diagnosis, duration of MS treatment, gestational age and weight of the newborn as relevant for specific pregnancy outcomes.

**The exploratory objectives** are:

6. To describe the following additional characteristics about pregnancy in cohorts 1 – 4:
  - Mode of delivery (CS/vaginal)
  - Preterm birth
  - Birth weight and LBW
  - Birth height and low birth height (LBH), according to country specific standards (FIN Sankilampi et al. 2013)
  - Birth weight (SGA and LGA), height and head circumference for gestational age (AGA)
  - Sex of the newborn
  - Head circumference and low head circumference (according to country-specific standards (FIN Sankilampi et al. 2013)
  - Apgar score (at 1 and 5 minutes)
  - Defect cases
  
7. To estimate the prevalence of i) congenital malformations in live or stillbirths, ii) ectopic pregnancies, iii) spontaneous abortions, and iv) stillbirths in the general population without MS diagnosis (cohort 6) in FIN, SWE, NOR for each pregnancy outcome separately as available in each country. The observed numbers of pregnancy outcomes in cohort 3, matched for age and country, are compared with the expected numbers through indirect standardisation under the assumption that cohort 3 had experienced the same prevalence as women in the general population without MS diagnosis (cohort 6).

## 9 Research methods

### 9.1 Study Design

The present study is a population-based cohort study using register data from three Nordic countries: FIN, SWE, NOR.

### 9.2 Setting

The target study population consists of Finnish, Swedish and Norwegian women with MS who have been pregnant during the study period. The study population will be identified according to the inclusion and exclusion criteria below.

#### 9.2.1 Inclusion criteria

- Women who have had a pregnancy with a recorded outcome consisting of an induced abortion, spontaneous abortion, ectopic pregnancy, or birth during the study period in FIN, SWE or NOR with the event being documented in the relevant databases.

#### 9.2.2 Exclusion criteria

- None

#### 9.2.3 Study period

The study periods in the different countries are as follows: FIN, 1 January 1996 – 31 December 2014; SWE, 1 July 2005 – 31 December 2014; NOR, 1 January 2004 – 31 December 2014. The start of the study period is determined by the availability of exposure data in each country. The end of the study period is determined by the availability of data on malformations. In FIN the follow-up period for the registration of MCA is 12 months after birth, in SWE 6 months. In NOR malformations are registered in the MBR and the newborns are followed until the end of the stay at the birth clinic (usually at least 4 days).

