### 9.2.4 Follow-up time

The cohort entry date (i.e. index date) is the date of LMP. This date is considered as the beginning of the pregnancy. The pregnancies are followed until induced abortion or birth. The births are followed-up for a maximum of 12 months for registration of MCAs (see section 9.2.3 Study period). Information on LMP, or gestational age, is not available for ectopic pregnancies or spontaneous abortions. The date of hospitalisation due to these outcomes will be used as a proxy of index date for these outcomes.

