#### **Prescription Registers (FIN, SWE, NOR)**

Information on maternal MSDMD exposure before and during pregnancy will be obtained from the Prescription Registers based on reimbursed drug purchases (information is linked to DPP in FIN). The Prescription Registers contain information on outpatient medication purchases in pharmacies (established FIN 1994, SWE 2005, NOR 2004). Prescription-only medicines are only sold in pharmacies, and dispensing requires a prescription issued by a physician or a dentist in FIN, SWE and NOR. In FIN, the register contains information on all purchased prescribed medicines that are reimbursed by the government. This excludes, for instance, most contraceptives. In SWE and NOR, all prescribed medicines purchased in community pharmacies are included irrespective of reimbursement status. The prescription data in the registers includes patient's ID, the generic name of the drug, ATC code, the brand name, the formulation and package, the amount as the defined daily dose (DDD), the date of purchase, the prescribing practice (primary vs. secondary healthcare), and the prescribing physician's area of specialisation.

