## Drugs and Pregnancy Project (FIN)

DPP will be a data source for the Finnish data regarding information on maternal MS diagnosis, MSDMDs, TOPFAs, live births, stillbirths, and MCAs. The purpose of the Finnish DPP, initiated in 2003, is to evaluate the pattern of drug use during pregnancy and estimate the effect of drug use on pregnancy outcomes. The research data are based on information obtained from the Finnish national health registers: the MBR, the Register on Induced Abortions and the Malformation Register, all maintained by THL (Artama et al. 2011). Information on maternal drug use and drug reimbursements is obtained from the Prescription Register and the Register on Reimbursed Medications, both maintained by the SII. The research database enables evaluation of the frequency and type of maternal drug use during pregnancy retrospectively from the year 1996 onwards (at the time of data extraction until the end of 2014). Drug purchases are recorded covering a time period from one month prior to pregnancy to the end of pregnancy in the DPP.

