### 9.4 Variables

**Exposures:** Maternal MS and related medication exposure before and during pregnancy are the basis of the exposure status of the study subjects in this study.

Pregnancies are considered unexposed if no MSDMDs of interest have been used within three months (except six months for mitoxantrone and cladribine) prior to LMP or during pregnancy. As the maximum reimbursable amount per purchase is the supply for three months of treatment, a pregnancy is defined as unexposed to MSDMDs if there are no purchases of MSDMDs within six months (except nine months for mitoxantrone and cladribine) prior to LMP or during pregnancy. Otherwise a pregnancy is defined as exposed to MSDMDs. Similarly, a pregnancy is defined as unexposed to IFN- $\beta$  if there have been no purchases of IFN- $\beta$  containing medications within six months prior to LMP or during pregnancy and otherwise a pregnancy is defined as exposed to IFN- $\beta$ .

The following MSDMDs and their ATC codes are included in this study: IFN- $\beta$ -1a (L03AB07), IFN- $\beta$ -1b (L03AB08), Peg IFN- $\beta$ -1-a (L03AB13), human normal immunoglobulin (J06BA02), cyclophosphamide (L01AA01), methotrexate (L01BA01, L04AX03), cladribine (L01BB04), mitoxantrone (L01DB07), alemtuzumab (L01XC04), glatiramer acetate (Copaxone®) (L03AX13), leflunomide (L04AA13), natalizumab (L04AA23), fingolimod (L04AA27), teriflunomide (L04AA31), azathioprine (L04AX01), dimethyl fumarate (N07XX09).

**Table 3: More detailed information on individual MSDMD agents, including information on availability and reimbursement in FIN, SWE and NOR.**

MSDMD agent	ATC code	Reimbursed in FIN in Jan 2015 (yes / no) 	Marketing authorisation date			Administration in hospital only 
			FIN	SWE	NOR	
IFN- $\beta$ natural	L03AB02		no	no	no	
IFN- $\beta$ -1-a	Avonex ®	yes	13.3.1997	13.3.1997	5.7.2002	no
	Rebif ®		4.5.1998	4.5.1998	19.8.2003	no
IFN- $\beta$ -1-b	Betaferon ®	yes	30.11.1995	30.11.1995	1.9.2006	no
	Extavia ®		20.5.2008	20.5.2008	20.5.2008	no
Peg IFN- $\beta$ -1-a	Plegridy ®	yes	18.7.2014	18.7.2014	18.7.2014	no
intravenous immunoglobulin	J06BA02	no	16.10.1991	10.10.1981	9.10.1996	yes
cyclophosphamide	L01AA01	no	4.6.1986	28.4.1959	6.4.1959	injection yes tablet no
methotrexate	L01BA01	yes  / no 	25.2.1981	23.6.1964	14.4.1971	tablet no
	L04AX03					infusion yes injection yes/no 

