### 9.7.6 Sensitivity analyses

- Lack of information on terminations of pregnancy due to foetal anomalies from SWE may yield underestimation of the prevalence of MCA in the study population. In FIN, 10.5% of total cases with MCAs were diagnosed and recorded in TOPFAs between 1993 and 2010. However, this may bias the study results on MCAs if the risk for TOPFA differs between women with different MSDMD exposures or MS exposure in SWE. Separate analyses will be performed on MCAs for the Norwegian and the Finnish data including pregnancy terminations, stillbirths and live births, and another analysis including live births only. The analyses will also be stratified by country as the follow-up times of the newborn babies for recording the malformations in MBRs or Malformation Register may vary between the countries.

- Information on pregnancy terminations is available from GW 12 onwards from the Norwegian data, and therefore, information on early pregnancy terminations conducted before GW 12 could result in incomplete data. Therefore separate analyses by trimesters on pregnancy terminations will be performed.
- In additional sensitivity analyses on MCAs, outcomes will be assessed where exposure occurred prior to pregnancy and through to the end of the first trimester of pregnancy. Also, an analysis of MCA outcomes from live births only will be performed.
- As there is a geographical variation in MS prevalence not only between countries but also within countries, descriptive statistics will be conducted by country and university hospital district level. Country and region will also be included in the multivariate analyses.
- Possible changes in diagnostic criteria and developments in examination and treatment throughout time, as well as trends in obstetric care may influence the estimated prevalence. The study periods also vary between the countries, which may reflect the deviation in the results. Therefore the year of pregnancy outcome will be taken into account in the descriptive statistics and analyses. By taking into account the data from 1 Jan 2005 to 31 Dec 2014 from each country (time period in which the data is available i.e. overlaps for all 3 countries), a separate sensitivity analysis of the primary objective will be provided as well.

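### Early Swedish and Norwegian pregnancies enter by outcome date without a full purchase look-back before LMP, so some exposed pregnancies can be classed as unexposed (moderate)

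*Protocol*

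**What the plan says.** - **Study period (9.2.3).** "The start of the study period is determined by the availability of exposure data in each country": Finland 1 January 1996, Sweden 1 July 2005, Norway 1 January 2004. Section 9.3.1.1 dates the prescription registers by year only: "established FIN 1994, SWE 2005, NOR 2004".
- **Eligibility (9.2.1, 9.2.2).** The unit admitted is defined by its outcome: "Women who have had a pregnancy with a recorded outcome consisting of an induced abortion, spontaneous abortion, ectopic pregnancy, or birth during the study period". There are no exclusion criteria.
- **Index date (9.2.4).** "The cohort entry date (i.e. index date) is the date of LMP".
- **Exposure (9.4).** A pregnancy is "defined as unexposed to MSDMDs if there are no purchases of MSDMDs within six months" before LMP or during pregnancy, with nine months for mitoxantrone and cladribine. The same six-month rule is applied to IFN-β alone.
- **Finnish source.** Section 9.3.1.2 names the DPP as a source for MSDMDs and adds: "Drug purchases are recorded covering a time period from one month prior to pregnancy to the end of pregnancy in the DPP". Table 2 also lists the National Prescription Register and the National Reimbursement Register as Finnish exposure sources.
- **Common-period analysis (9.7.6).** It is described as the period in which all three countries have data: "By taking into account the data from 1 Jan 2005 to 31 Dec 2014 from each country".
- **Swedish start.** The abstract, section 9.2.3 and Table 5 give 1 July 2005. The text of section 9.5 gives 1 January 2005.

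**The concern.** Eligibility is anchored on the end of pregnancy, while exposure is read from a window that begins six months before the start of pregnancy. Where the study period opens when purchase data open, the earliest pregnancies have a window that the register cannot see, and the classification rule reads an unseen purchase as no purchase. The unseen part matters: section 7 says that discontinuation should be considered once a woman becomes pregnant, so purchases before LMP may be the only trace of exposure at conception.

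At stake are both primary comparisons (cohort 1 against cohorts 3 and 4) and the prevalence in unexposed women that the CHMP requested. Section 9.9 does not list the gap as a limitation. Adjustment for country and year in section 9.7.3 does not repair a misclassified exposure.

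**Working it through.** **1. The protocol's own figure.** Inputs from section 9.5: n1 = 294 (cohort 1), n0 = 1270 (cohort 3), background p0 = 24/331 = 0.0725, two-sided 5%, 80% power.

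Power = Φ[(Δ − 1.96 × SE pooled) / SE unpooled]. At RR 1.72, p1 = 0.1247 and Δ = 0.0522; SE pooled = 0.01779 and SE unpooled = 0.02060. Then (0.0522 − 0.0349)/0.0206 = 0.84, so power is 80%. The stated 1.72 reproduces (1.717 if p0 is rounded to 7.3%).

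**2. Length of window needed.** Section 2 puts delivery at about 280 days from LMP. With six months (183 days) of look-back: 280 + 183 = 463 days, about 15 months. If exposure data begin with the study period, the first fully covered term birth is about 7 October 2006 in Sweden and 8 April 2005 in Norway.

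**3. Pregnancies affected.** Accrual from section 9.5, assumed even over time:
- Sweden: 329/6.5 = 51 per year × 1.25 years = 64 (13% of 482).
- Norway: 412/11 = 37.5 per year × 1.25 years = 47 (11% of 412).
- Total 111 of 1671 = 6.6%. Using 463 days exactly gives 111.6, or 6.7%.

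Of these, (280/365.25) × (50.6 + 37.5) = about 68 have LMP before the data begin, so no pre-LMP purchases are visible at all. If every pregnancy ended at 12 weeks (84 + 183 = 267 days), the affected total would be about 64.

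**4. Sensitivity to the Swedish register date.** If Swedish purchases were available from 1 January 2005, 181 days earlier, the shortfall for a birth on 1 July 2005 would still be 463 − 181 = 282 days, or 50.6 × 282/365.25 = about 39 Swedish pregnancies. The gap shrinks but stays.

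**5. Ceiling on misclassification.** Section 9.5 expects 22% exposed to IFN-β. 0.22 × 111.6 = 24.6 pregnancies, or 24.6/1270 = 1.9% of cohort 3. This assumes that none of them has a purchase in the visible part of the window.

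**6. Effect on the RR.** Take true RR 1.72 and p0 = 7.3%. Observed cohort 3 prevalence = 0.073 × (1 + 0.72 × 0.0193) = 0.0740. Apparent RR = 1.72 × 0.073/0.0740 = 1.70. Power falls to about 76% if all 25 are also lost from cohort 1. At a true RR of 1 this mechanism produces no bias.

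**7. Cost of requiring the full six-month look-back.** 1671 − 112 = 1559 pregnancies; cohort 1 = 294 × 1559/1671 = 274; cohort 3 = 1270 × 1559/1671 = 1185. By the formula in step 1 with p0 = 7.3%, the minimum detectable RR is about 1.74, and power at RR 1.72 is about 78%.

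**8. Common-period analysis.** 1 January 2005 precedes the Swedish start by six months. In Norway, a term birth on that date is 463 − 366 = 97 days short of a full window. The analysis therefore does not close the gap in either country.

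**The case against.** The strongest reply is that the effect is small and partly self-correcting. Any purchase in the visible part of the window makes a pregnancy exposed, so assignment to the unexposed cohorts is not automatic and 24 to 25 is a ceiling. Even accrual may also overstate the early counts. In Finland there were 86 MS pregnancies in 2010 against (433 − 86)/14 = about 25 per year before; no yearly figures are given for Sweden or Norway. All of this stands and limits the severity. It does not remove the defect.

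Three stronger readings are tempting and are not supported:

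- **Finland.** A reader might infer from the one-month DPP window that all 777 planned Finnish pregnancies lack the look-back. Table 2 lists the National Prescription Register as well, and that register dates from 1994, before the 1996 start. What is missing is a sentence saying which source governs the six-month window.
- **Direction.** A reader might infer that every error loads the comparators. A missed purchase of another MSDMD in an IFN-β user instead moves the pregnancy from the unstudied both-exposed cell of Table 1 into cohort 1.
- **Pregnancies before diagnosis.** With no timing rule and no exclusions, a reader might infer that a woman diagnosed late contributes her earlier births and that this pushes the RR away from 1. The protocol is silent. The target population of women with MS and the covariate for time since diagnosis may presume a prior diagnosis. Such pregnancies would be truly unexposed, so the issue would be comparability and not missed purchases. No figure in the protocol gives their share, so no effect can be calculated.

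**Conclusion.** The look-back defect holds for Sweden and Norway. It follows from combining outcome-based entry, a start date set by exposure data, and a rule that reads no purchase as unexposed. About 111 pregnancies (6.6% of the total) have an incomplete window. At most 24 to 25 are misclassified, with mild attenuation (1.72 to about 1.70). These sizes rest on even accrual, term pregnancies, 22% exposure and purchase data starting with the study period. The register dates are given by year only, but step 4 shows that the conclusion does not depend on the exact day.

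Severity is moderate. The bias is small, but it is built into eligibility, it is undisclosed, and it is cheap to remove. The planned common-period analysis does not repair it, and the Swedish start date contradicts itself within the protocol. The timing of MS diagnosis is a secondary point of unknown size.

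**What to change.** 1. **Sections 9.2.1 and 9.2.3.** For Sweden and Norway, include a pregnancy only if its full look-back falls after national prescription data begin: six months before LMP, and nine months where mitoxantrone or cladribine is classified. If data begin on the stated study start dates, the six-month rule means LMP from 1 January 2006 in Sweden and from 1 July 2004 in Norway. Give the exact register start dates.
2. **Outcomes without LMP.** For spontaneous abortions and ectopic pregnancies, apply the same rule to LMP approximated with the 9 and 8 weeks already used in section 9.9.
3. **Section 9.7.6.** Reconcile 1 January and 1 July 2005 across sections 9.2.3, 9.5 and 9.7.6. Start the common-period analysis at the first LMP date with full look-back in all three countries.
4. **Finland.** State that MSDMD purchases for the six-month window come from the National Prescription Register and not from the DPP extract.
5. **MS diagnosis.** State that the first MS record in the sources of Table 2 must be on or before LMP, or show pregnancies before diagnosis separately.

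**Cost.** The six-month rule loses about 111 pregnancies and moves the minimum detectable RR from 1.72 to about 1.74. A nine-month window applied to every pregnancy would affect about 88.1 × 554/365.25 = 134. The number lost to a diagnosis rule cannot be derived from the protocol. Settle the wording before permit applications go out (one month after registration, section 6), because a purchase window extracted too short cannot be recovered in the analysis.
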